3.9 Outcomes

3.9.1 Primary outcome

The primary outcome is a composite of any stroke or death within 30 days after enrollment or ischemic stroke in the territory of the qualifying artery from 30 days to 1 year after enrollment.

Ischemic stroke is defined as a new focal neurological deficit of sudden onset persisting for at least 24 hours and confirm by cerebral infarction on CT or MRI. Ischemic stroke are further classified as being either in or out of the territory of the qualifying artery. We regard ischemic stroke either in or out of the territory of the qualifying artery within 30 days after enrollment as a primary outcome, but beyond 30 days through 1 year, only ischemic stroke in the territory of the qualifying artery is considered as a primary outcome. We define symptomatic intracranial hemorrhage (sICH) as parenchymal, intraventricular, or subarachnoid hemorrhage identified on brain MRI or CT, which led to new emergence or worsening of neurological symptoms lasting more than 24 hours or a seizure. Death is categorized as vascular-related or non-vascular-related, and all-cause death is considered a primary outcome within 30 days.

Ischemic stroke and intracranial hemorrhage will be determined by core-lab assessment of imaging, and neurological assessment will be performed at the study site by independent neurologist certified in NIHSS, adjudication of outcomes will be done by an outcome adjudication committee.

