3.9.2 Secondary outcomes

Secondary outcomes as follows:

- Mortality within 1 year;
- Ischemic stroke outside the territory of the qualifying artery within 1 year;
- Disabling stroke within 1 year;
- TIA in the territory of the qualifying artery within 1 year;
- Unplanned revascularization (EC-IC bypass surgery or ER) of the qualifying artery within 1 year;
- Myocardial infarction within 1 year;
- Composite vascular events within 1 year;
- Quality of life assessment (EuroQol -Five-Dimensions [EQ-5D] scale questionnaire) at 1 year;
- mRS score at 1 year;
- Periprocedural outcomes;
- Restenosis or reocclusion (symptomatic or asymptomatic).

Disabling stroke is defined by any of the following: (1) an mRS score of 3 or more, (2) an increase of at least 1 point in the mRS score from prestroke baseline, (3) a score on the composite NIHSS of 7 or more, or (4) an increase of at least 4 points in the NIHSS score from pre-stroke baseline.

TIA is defined as duration of a focal or global neurological deficit <24 hours, any variable neuroimaging does not demonstrate a new hemorrhage or infarction.

Composite vascular events within 1 year included any stroke, myocardial infarction, and unplanned revascularization within 1 year.

Periprocedural outcomes are: (1) successful recanalization rate, (2) periprocedural complications: in-stent thrombosis, distal embolization, symptomatic intracranial hemorrhage, parenchymal hematoma type 2 (defined by the Heidelberg classification³⁴), arterial dissection, arterial perforation, (3) residual stenosis, (4) NIHSS score at 24-72 hours, (5) death within 7 days.

Restenosis is defined as >50% stenosis within or immediately adjacent (within 5 mm) of the treated segment and >20% absolute luminal loss, reocclusion is defined as total occlusion of the target artery segment.

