5.1. Primary Outcome

The primary outcome is a composite of any stroke or death within 30 days after enrollment or ischemic stroke in the territory of the qualifying artery from 30 days to 1 year after enrollment.

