5.2. Secondary Outcomes

The secondary outcomes are as follows:

- (1) Mortality within 1 year;
- (2) Ischemic stroke outside the territory of the qualifying artery within 1 year;
- (3) Disabling stroke within 1 year;
- (4) Transient ischemic attack (TIA) in the territory of the qualifying artery within 1 year;
- (5) Unplanned revascularization (extracranial-intracranial [EC-IC] bypass surgery or ER) of the qualifying artery within 1 year;
- (6) Myocardial infarction within 1 year;
- (7) Composite vascular events within 1 year, including any stroke, myocardial infarction, and unplanned revascularization;
- (8) Quality of life assessment (EuroQol-Five-Dimensions [EQ-5D] scale questionnaire) at 1 year;
- (9) Modified Rankin Scale (mRS) score at 1 year;
- (10) Periprocedural outcomes, including the successful recanalization rate, periprocedural complications, residual stenosis, National Institute of Health Stroke Scale (NIHSS) score at 24-72 hours, death within 7 days, etc;
- (11) Restenosis or reocclusion (symptomatic or asymptomatic).

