7.2 Data Handling Conventions

Premature withdrawal and missing data

If any subject withdraws prematurely from the study (prior to the final visit), they are required to complete the withdrawal visit in the case report form (CRF). The reasons for withdrawal will be presented in a summary table. For the purposes of summaries and analysis of clinic visit data, this visit will be assigned to the next scheduled clinic visit for that subject, regardless of whether the date falls within the next visit window.

Efforts will be undertaken at study sites to reduce the amount of missing data. For the primary efficacy outcome, multiple imputations in a model including strong prognostic variables will be used. Also, sensitivity analyses will be undertaken to explore the effect of missing data on the endpoint and test the robustness of the estimate. Ultimately, only patients who entirely completed the 1-year follow-up are included in the final analysis.

Event rates

The number of people and person-time of events should be recorded in detail and showing the event rate of each treatment group in summary statement.

The event rate for each treatment group will be calculated as: the sum of number of event for all the patients/the sum of number of treatment periods for all the patients.

Time to event analysis

Differences between treatments in the risk of any stroke (ischemic or haemorrhagic) event or composite vascular events during follow-up will be assessed using standard Kaplan-Meier time-to-event approaches. The time to the first event will be used in the model when there are multiple events of the same type. Patients will be considered censored at the time of study termination or death if there are no events occurred during the study.

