7.7 Secondary Outcomes

Time-to-event secondary outcomes will be evaluated using Kaplan-Meier survival analysis and Cox regression model. HR between the two groups and its 95% CI will be calculated using a Cox proportional hazards regression model. Non-time-endpoints of the secondary outcomes will be evaluated using logistic regression model. The 1-year mRS score will be analyzed using ordinal logistic regression to estimate the common odds ratio (OR). The 1-year EQ-5D scores will be compared between groups using general linear regression analysis.

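### Censoring at death makes one minus Kaplan-Meier slightly overstate 1-year incidence for endpoints without death, and the vascular composite leaves out some vascular deaths

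*SAP*

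**What the plan says.** The censoring rule is in the time-to-event paragraph of SAP 7.2: "Patients will be considered censored at the time of study termination or death if there are no events occurred during the study". That paragraph opens with two endpoints: "Differences between treatments in the risk of any stroke (ischemic or haemorrhagic) event or composite vascular events during follow-up will be assessed" by Kaplan-Meier methods. No other censoring rule appears in either document. SAP 7.7 (Secondary Outcomes) adds: "Time-to-event secondary outcomes will be evaluated using Kaplan-Meier survival analysis and Cox regression model". Protocol 3.16.2 and SAP 7.5 (Primary Efficacy Outcome) use Kaplan-Meier, log-rank and Cox for the primary outcome. The Statistical Methods entry of the Protocol Synopsis says that the curves are there to display incidence over time.

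The vascular composite has the same three components in both documents. Protocol 3.9.2: "Composite vascular events within 1 year included any stroke, myocardial infarction, and unplanned revascularization within 1 year". SAP 5.2: "Composite vascular events within 1 year, including any stroke, myocardial infarction, and unplanned revascularization". Death is not among them.

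Protocol 3.9.1 says: "Death is categorized as vascular-related or non-vascular-related, and all-cause death is considered a primary outcome within 30 days". No listed outcome or analysis then uses the vascular/non-vascular split. All-cause mortality within 1 year is a separate secondary outcome.

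**The concern.** Two separate issues arise.

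The first is estimation. When death is censored, Kaplan-Meier treats a patient who has died as someone who could still have had the event later. One minus the curve is then the risk in a hypothetical population without deaths, not the proportion of patients who actually had the event by 1 year. A reader who takes the curve as incidence reads a figure that is too high.

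The second is definition. A sudden vascular death, or a fatal bleed outside the brain, falls under none of the three composite components. Nor, read literally, does an ischemic stroke that is fatal within 24 hours or never imaged, because Protocol 3.9.1 requires a deficit of at least 24 hours and an infarct on CT or MRI. Procedural deaths can occur only among patients who undergo recanalization, and the Protocol Background acknowledges elevated procedural risk. Such deaths could therefore be unevenly split between the groups.

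**Working it through.** **No figure to reproduce.** The documents give no event rate, mortality rate, sample size or power that bears on this point. All rates below are assumptions.

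**Step 1: which endpoints are affected.** The rule matters only for time-to-event endpoints that do not include death: the primary outcome after day 30, out-of-territory ischemic stroke, disabling stroke, TIA, myocardial infarction, unplanned revascularization and the vascular composite. The censoring paragraph names only any stroke and the composite. Applying it to the others is an inference, based on the shared methods and the absence of any other rule. Mortality is not affected. The 1-year mRS scores death as 6 (Protocol Appendix 1).

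**Step 2: size of the overstatement.** Take constant hazards. Let r be the 1-year event risk with death censored and d the corresponding 1-year risk of death without a prior event.

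- h = −ln(1 − r) and g = −ln(1 − d)
- One minus Kaplan-Meier = r
- Cumulative incidence = h/(h + g) × [1 − exp(−(h + g))]

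Worked case, r = 10% and d = 5%: h = 0.1054, g = 0.0513 and h + g = 0.1567. Then 1 − exp(−0.1567) = 1 − 0.90 × 0.95 = 0.145. Cumulative incidence = (0.1054/0.1567) × 0.145 = 0.0975. Kaplan-Meier gives 10.0% against an actual 9.75%, an excess of 0.25 points.

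Excess in percentage points:

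| Event risk r | d = 2% | d = 5% | d = 10% |
|---|---|---|---|
| 5% | 0.05 | 0.13 | 0.25 |
| 20% | 0.19 | 0.49 | 0.98 |

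The 10% column is a stretch case: eligibility requires mRS 0-2 and age 18 to 80, and excludes life expectancy under 1 year. For the primary outcome the excess is smaller than these full-year figures suggest, because a death by day 30 is itself an event and only later deaths compete.

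**Step 3: effect on the comparison.** Take r = 10% in both groups, with d = 6% in one and 2% in the other. One minus Kaplan-Meier is 10.0% in both.

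- At d = 6%: (0.1054/0.1672) × (1 − 0.90 × 0.94) = 9.70%
- At d = 2%: (0.1054/0.1256) × (1 − 0.90 × 0.98) = 9.90%

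Cumulative incidence describes what happened, but deaths lower it slightly in the group that has more of them. It does not answer the question about missing vascular deaths; only an endpoint that counts them does.

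**Step 4: what counting those deaths could do.** Take a medical-group composite risk of 10% (h = 0.1054) and a hazard ratio of 0.70 with deaths censored, so the ER hazard is 0.0738. Adding vascular deaths with no prior component event gives HR = (0.0738 + g_ER)/(0.1054 + g_Med).

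- 3% ER, 1% medical: (0.0738 + 0.0305)/(0.1054 + 0.0101) = 0.90
- 2% in each: (0.0738 + 0.0202)/(0.1054 + 0.0202) = 0.75
- 1% ER, 3% medical: (0.0738 + 0.0101)/(0.1054 + 0.0305) = 0.62

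These are hazard ratios for a different endpoint, not corrections of an error. They show that the choice of endpoint can matter more than the Kaplan-Meier excess, and in either direction.

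**Step 5: a conflict within SAP 7.2.** The missing-data paragraph ends by limiting the final analysis to patients who completed the whole 1-year follow-up. Read literally, that removes patients who die, whereas the censoring sentence keeps them up to the date of death. Both cannot apply.

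**The case against.** The plan has a good defence on most of this. Log-rank and Cox analyses with censoring at death are standard cause-specific inference, so nothing here invalidates the primary comparison. The Kaplan-Meier excess is small. Stroke, infarction and revascularization form a legitimate composite, stated identically in both documents. With enrolment running from 2020 to 2023, replacing it now would look like a post hoc endpoint change. All of that stands.

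A reader might infer that every vascular death is scored as event-free. The documents do not support this. A fatal stroke or infarction that meets its definition is already a component event. Any other such patient is censored at death and leaves the risk set; the patient is not carried event-free to 1 year. Nor are these deaths hidden: they count in 1-year mortality, in mRS 6, as serious adverse events and, to day 30, in the primary outcome.

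A reader might also infer that Kaplan-Meier flatters the group with more deaths. Step 3 shows otherwise: at equal event hazards it gives both groups the same figure.

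What remains is that the curves are presented as incidence without a method that estimates it, and that the death classification is collected but unused.

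**Conclusion.** The point holds as a modest, inexpensive improvement in reporting. For the endpoints in Step 1, one minus Kaplan-Meier overstates 1-year incidence by about 0.05 to 0.5 percentage points at assumed mortality of 2-5% and event risk of 5-20%, and by less for the primary outcome. This rests on constant hazards and assumed rates. The hazard ratios and log-rank tests remain valid as cause-specific comparisons.

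The composite's omission is narrower than it first appears: vascular deaths with no earlier qualifying component event. How many there will be, and how they will split between groups, cannot be known from the documents. That supports a supplementary analysis, not a redefinition.

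**What to change.** 1. In SAP 7.2, for time-to-event endpoints that do not include death (for the primary outcome, deaths after day 30), plot and quote Aalen-Johansen cumulative incidence with death as a competing event. Label the Cox estimate a cause-specific hazard ratio. Do the same in the matched cohort, since SAP 7.6 (Propensity Score Matching Analysis) keeps the methods unchanged after matching.
2. Keep the composite as defined in Protocol 3.9.2 and SAP 5.2. Add a supplementary analysis that also counts adjudicated vascular death, labelled as added after the composite was defined.
3. Reconcile the censoring sentence with the completers-only sentence in SAP 7.2, so that patients who die stay in the analysis.

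The cost is a few sentences in the SAP and one extra analysis. No new data are needed, because deaths are already classified. Quoted incidences will fall slightly.

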7.3 Study Population

The number of all participants included in the screening will be calculated. Listing will be presented for participants of deviations from the inclusion/exclusion criteria, the reasons for screening failures will also be documented. Based on all enrolled participants, the number and percentage of participants who completed the study and withdrew early, the number and percentage of participants who withdrew early for various reasons, as well as the number of participants who lost to 1-year follow-up, will be calculated and summarized. Finally, participant distribution flow chart will be presented.

7.4 Demographic and Baseline Characteristics

The following demographic information baseline characteristics, such as age, sex, medical history, smoking history, alcohol history, treatment history, qualifying ischemic event characteristics, Alberta Stroke Program Early CT Score (ASPECTS) for anterior circulation stroke as well as posterior circulation ASPECTS (pc-ASPECTS), baseline mRS score and NIHSS score, will be listed and summarized for subjects in each treatment group.

The continuous data followed normal distribution will be presented as mean and standard deviation, and the continuous data followed skewness distribution will be presented as median and interquartile range; categorical data will be presented as n (%). T-test or Wilcoxon-Mann-Whitney test will be used for comparison between two continuous data, and Chi-squared tests, Fisher exact test will be used for comparison between two categorical data.

7.5 Primary Efficacy Outcome

The difference in primary outcome between groups was assessed using Kaplan-Meier analysis and compared via log-rank test. Hazard ratio (HR) between the two groups and its 95% CI will be calculated using a Cox proportional hazards regression model. Furthermore, a multivariate Cox proportional hazards model will be used to perform multivariable adjustment for the primary outcome, yielding the adjusted hazard ratio (aHR) and its 95% CI.

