Secondary Endpoints	
Secondary outcomes as follows:
 
 • Mortality within 1 year; • Ischemic stroke outside the territory of the qualifying artery within 1 year; • Disabling stroke within 1 year; • TIA in the territory of the qualifying artery within 1 year; • Unplanned revascularization (EC-IC bypass surgery or ER) of the qualifying artery within 1 year; • Myocardial infarction within 1 year; • Composite vascular events within 1 year, including any stroke, myocardial infarction, and unplanned revascularization; • Quality of life assessment (EuroQol-5-Dimensions scale questionnaire) at 1 year; • mRS score at 1 year; • Periprocedural outcomes; • Restenosis or reocclusion (symptomatic or asymptomatic).
Statistical Methods	
 • Categorical variables will be compared between treatment groups using χ^2 or Fisher's exact test. Continuous variables or ordinal variables will be compared between treatment groups using t-test or Wilcoxon-Mann-Whitney test. • The primary and time-to-event secondary outcomes will be compared between the groups using log-rank test. • Kaplan-Meier curves will be used to show the incidence of outcomes over time. • The hazard ratio (HR) and adjusted hazard ratio (aHR) between groups, along with their 95% CIs, will be determined using univariate and multivariate Cox proportional hazards regression models. • Propensity score matching (PSM) will be performed to reduce the possible influence of selection bias and confounders on the outcomes. • A 2-sided P value less than 0.05 is considered to demonstrate a statistically significant difference. • All analyses will be performed with using SAS Version 9.4.

Schedule of assessments

Table 1: Summary of Study Treatment and Study Assessments

Study Requirements	Screening and Baseline	Endovascular recanalisation			Discharge	Follow-up Visits		
		Pre-procedure	Intra-procedure	Post-procedure		30-Day (±7 days)	90-Day (±7 days)	1-Year (±30 days)
Inclusion/Exclusion	X	X						
Informed Consent	X							
Clinical Assessment, Vital Signs, and Physical Exam	X	X			X	X	X	X
Laboratory tests	X					X	X	X
NIHSS (blinded to treatment)	X				X	X		
mRS (blinded to treatment)	X				X	X	X	X
EQ-5D (blinded to treatment)						X	X	X
mTICI assessment		X	X	X				
CT/MRI	X			X			X	X
CTP/PWI	X						X	X
CTA/DSA	X						X	X
Protocol Deviations		X	X	X	X	X	X	X
Medication review and patient compliance survey	X	X	X	X	X	X	X	X

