3.1 Study Design

The Endovascular Recanalization for Non-Acute Intracranial Artery Occlusion (ERNA-IAO) study is a multicenter, prospective, cohort study, this cohort prospectively will enroll consecutive patients with radiologically confirmed sNA-IAO at 6 comprehensive stroke centers in China from January 1,2020 to October 31, 2023. All participants or their legal representatives provide written informed consent before enrollment. The primary objective of this study is to evaluate whether ER plus medical treatment is superior to medical treatment alone for patients with sNA-IAO presenting beyond 24 hours after symptom onset. All study centers complied with the Expert Consensus on Standardized Diagnosis and Treatment in China, ensuring consistent data acquisition across sites. The study protocol was approved by the Institutional Ethics Committee of Beijing Tiantan Hospital (approval number: KY2020-114-02), and each subcenter, and will follow the Strengthening the Reporting of Observational Studies in Epidemiology (STROBE) guideline.

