3.6 Treatments and Study Groups

The technical feasibility of endovascular recanalization for all sNA-IAO patients in this study will be collaboratively evaluated by two experienced interventional neuroradiologists. The decision to select either medical treatment alone or additional ER is made by the patients themselves or their legal representatives. Patients are subsequently divided into two groups according to the treatment they received: the medical group and the endovascular recanalization (ER) group. Patients in ER group will receive endovascular recanalisation procedure (details in procedure part below) plus medical treatment (same as the control group).

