3.16.4 Propensity score matching analysis

Propensity score matching (PSM)³⁵ will be performed to reduce the possible influence of selection bias and confounders on the outcomes. A PSM cohort will be established in a 1:1 ratio based on the nearest-neighbor matching algorithm with a caliper width of 0.2 of the propensity score with main variables associated with the primary outcome as covariates. Statistical analysis methods for baseline characteristics and outcome will remain consistent before and after PSM.

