To investigate whether endovascular recanalisation plus medical treatment is superior to medical treatment alone for symptomatic non-acute intracranial artery occlusion (sNA-IAO) in the primary outcome (any stroke or death within 30 days after enrollment or ischemic stroke in the territory of the qualifying artery from 30 days to 1 year after enrollment).

3. Statistical Hypotheses

The primary hypothesis is:

Patients in the endovascular recanalisation group are expected to demonstrate a lower incidence of primary outcome (any stroke or death within 30 days after enrollment or ischemic stroke in the territory of the qualifying artery from 30 days to 1 year after enrollment).

4. Study Design

The Endovascular Recanalization for Non-Acute Intracranial Artery Occlusion (ERNA-IAO) study is a multicenter, prospective, cohort study, this cohort prospectively enrolls consecutive patients with radiologically confirmed sNA-IAO at 6 comprehensive stroke centers in China from January 1, 2020 to October 31, 2023. All study centers were required to have performed at least 120 endovascular procedures annually, including at least 40 cases of endovascular interventions involving intracranial arteries. The interventional neuroradiologists at these centers had each performed over 100 endovascular procedures. All participants or their legal representatives provide written informed consent prior to enrollment. The technical feasibility of endovascular recanalization for all sNA-IAO patients in this study will be collaboratively evaluated by two experienced interventional neuroradiologists. The decision to select either medical treatment alone or additional endovascular recanalization is made by the patients themselves or their legal representatives. Patients are subsequently divided into two groups according to the treatment they received: the medical group and the endovascular recanalization group. The study protocol was approved by the Institutional Ethics Committee of Beijing Tiantan Hospital, (approval number: KY2020-114-02), and each subcenter, and will follow the STROBE (Strengthening the Reporting of Observational Studies in Epidemiology) guideline.

Endovascular recanalization (ER):

Patients will receive ER (details in procedure part in Supplement 1) plus medical treatment (same as the control group). All procedures are performed under general anesthesia by an experienced interventional neuroradiologist.

Medical treatment:

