7.1 General Considerations for Data Analyses

All analyses will be performed with using SAS Version 9.4. All analysis output will use the following treatment group naming conventions and treatment order:

ER group: patients will receive ER (details in procedure part) plus medical treatment (same as the control group);

Medical group: patients will receive the medical treatment alone.

All statistics is two sided with a $P < 0.05$ considered significant.

Examination of Subgroups

The rates of the primary outcome will be presented for each level of the covariates listed below. We will assess the extent to which the treatment effect varies across levels of each subgroup using interaction tests.

Multiple Comparisons and Multiplicity

A single primary efficacy variable has been defined for this study, with all other efficacy variables identified as secondary or other. Similarly, only one treatment comparison is of interest in the study and therefore there are no requirements to adjust for multiple comparisons or multiple endpoints within this study.

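### Patients choose their treatment, but the plan does not say whether the unadjusted log-rank test, the adjusted hazard ratio or the matched result decides superiority

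*SAP*

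**What the plan says.** **Allocation.** SAP section 4 (Study Design): "The decision to select either medical treatment alone or additional endovascular recanalization is made by the patients themselves or their legal representatives". Protocol 3.6: "Patients are subsequently divided into two groups according to the treatment they received".

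**Aim.** Protocol 3.1: "The primary objective of this study is to evaluate whether ER plus medical treatment is superior to medical treatment alone". Significance is two-sided P<0.05 (Protocol 3.16.5, SAP 7.1). The rule is not attached to any particular analysis.

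**Analyses of the primary outcome.**
- Unadjusted comparison. SAP 7.5 (Primary Efficacy Outcome): "The difference in primary outcome between groups was assessed using Kaplan-Meier analysis and compared via log-rank test". Protocol 3.16.2 says the same, and the Protocol Synopsis (Statistical Methods) says: "The primary and time-to-event secondary outcomes will be compared between the groups using log-rank test". A univariate Cox hazard ratio goes with it.
- Multivariable Cox adjusted hazard ratio (Protocol 3.16.2, SAP 7.5). No covariates are listed.
- 1:1 propensity score matching, intended to reduce selection bias and confounding (Protocol 3.16.4; SAP 7.6, Propensity Score Matching Analysis). "Statistical analysis methods for baseline characteristics and outcome will remain consistent before and after PSM".

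**Secondary outcomes.** SAP 7.7 (Secondary Outcomes): "The 1-year mRS score will be analyzed using ordinal logistic regression to estimate the common odds ratio (OR"). A general linear model is planned for EQ-5D. No covariates are stated for either full-cohort model.

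**The concern.** In a self-selected cohort the full-cohort log-rank test measures the treatment effect plus any prognostic difference between those who chose recanalization and those who did not. The plan recognises this, since it includes adjustment and matching. It does not rank the three results.

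Two things are at stake. First, the unadjusted P value is eligible to decide superiority, and it is the analysis least able to do so here. Second, if the three results disagree, nothing in the plan settles which one stands, so the choice could be made once the results are known. The documents do not say which way patients selected. The error could therefore be a false benefit, a false harm, or a real benefit that is missed.

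**Working it through.** **1. Is any analysis designated?** I compared the Protocol Synopsis, Protocol 3.16.2, 3.16.4 and 3.16.5, and SAP sections 3, 7.1, 7.5 (Primary Efficacy Outcome) and 7.6 (Propensity Score Matching Analysis). The SAP hypothesis predicts a lower incidence with recanalization but ties no test or estimate to it. None of these places calls the log-rank, the adjusted hazard ratio or the matched result primary, confirmatory, supportive or sensitivity. None gives a rule for disagreement. The omission is the same in both documents.

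**2. Inputs for an illustration.** The documents give no sample size, power, event rate, allocation ratio or imbalance, so there is no figure to reproduce. All inputs here are assumptions: N = 400, 12% one-year risk, hence D = 400 × 0.12 = 48 events, roughly equal groups, true HR 1. Let b be the log-HR per SD of a prognostic score and d the difference in mean score between groups in SD.

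**3. Approximation.** The apparent log-HR is about b × d. The log-rank statistic is shifted by s = √(D/4) × b × d = 3.464 × b × d. Two-sided rejection is Φ(−1.96 + s) + Φ(−1.96 − s).

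| b | d | s | approximate rejection | simulated rejection |
|---|---|---|---|---|
| any | 0 | 0 | 5.0% | about 5% |
| 0.2 | 0.47 | 0.326 | 6.2% | about 6% |
| 0.2 | 0.70 | 0.485 | 7.7% | about 8% |
| 0.4 | 0.47 | 0.651 | 10.0% | about 9-10% |
| 0.4 | 0.70 | 0.970 | 16.3% | about 16-17% |
| 0.7 | 0.47 | 1.140 | 20.7% | about 18-21% |
| 0.7 | 0.70 | 1.697 | 39.7% | about 36-38% |

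The simulation used exponential event times, logistic treatment choice on the score and censoring at one year. It included no dropout.

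**4. A second route.** Take one binary risk factor, present in 30% of recanalization and 50% of medical patients, with HR g and true treatment HR 1. The crude HR is (1 + 0.3(g − 1)) / (1 + 0.5(g − 1)). For g = 2 this is 1.3/1.5 = 0.87, and for g = 3 it is 1.6/2.0 = 0.80. With 60 assumed events, s = √15 × ln(crude HR), and rejection is 8.6% and 13.9%. In a simulation of 400 patients with g = 3, rejection was 14.2% unadjusted, 4.2% adjusted and 3.8% matched.

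**5. Direction.** When lower-risk patients choose recanalization, almost all the excess rejections favour it. When higher-risk patients choose it, they point to harm. With b = 0.7 and d = 0.47 in that second direction, about 0.1% or fewer of cohorts falsely favour recanalization.

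**6. Masked benefit.** Take true HR 0.5, untreated risk 12% (34-35 events), b = 0.7, and higher-risk patients choosing recanalization. At d = 0.47 and 0.70, power is 17.5% and 8.0% for the unadjusted log-rank, against 49.6% and 46.5% for the multivariable Cox model.

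**7. What adjustment does.** In the HR 1 settings with all confounders measured and 13 model terms, the multivariable Cox model rejects in 4.4-6.0%. When an unmeasured confounder (log-HR 0.4, slope of choice 0.4 in the same direction) is added to strong measured confounding, the unadjusted test rejects in 51.7%. The Cox model then rejects in 7.4%, with an HR of 0.85.

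**The case against.** **Confounding is already addressed.** This is largely right. Adjustment and matching are both prespecified, and matching has the stated purpose of reducing selection bias. A reader might infer that the plan ignores confounding, and the documents do not support that. What is missing is the rank of the analyses.

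**The log-rank test is primary by position.** A reader might infer this because it comes first in Protocol 3.16.2 and SAP 7.5 and is the test named in the Synopsis. No text says so. If it were so, the unadjusted test would certainly decide, which is worse than the gap described here.

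**Three analyses at 0.05 make a multiplicity error.** A reader might infer that SAP 7.1 is wrong to waive adjustment, where it says: "Similarly, only one treatment comparison is of interest in the study and therefore there are no requirements to adjust for multiple comparisons". The documents do not support that. SAP 7.1 concerns endpoints and treatment comparisons, and there is one of each. The three analyses are highly correlated. Without confounding, at least one rejects in only 5.5-6.2% of simulated cohorts. The excess under confounding comes almost wholly from bias in the unadjusted test.

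**The figures are assumed, and the good performance of adjustment is partly built in.** Both points stand. The upper end near 38% needs a strong prognostic score and a large imbalance together. Near-nominal adjusted error is expected when every confounder is measured and the model is correct. The omission itself does not depend on these figures.

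**Conclusion.** The concern holds in this form. Treatment is self-selected, the only named between-group test of the primary outcome is unadjusted, and neither document says which of the unadjusted, adjusted and matched results decides superiority. The plan does not say that the unadjusted P value decides, but it allows that.

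Under the assumptions N = 400, 12% risk and true HR 1, that test rejects in about 5% of cohorts without imbalance. At 0.47-0.70 SD imbalance it rejects in about 6-8%, 9-17% or 18-38% for a prognostic log-HR of 0.2, 0.4 or 0.7 per SD. These are two-sided rates. They amount mostly to false superiority only if lower-risk patients choose recanalization. The real imbalance, event count and direction of selection are not in the documents, so where this study would fall in that range is unknown.

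This should be settled before the groups are compared, because it determines what the main conclusion rests on.

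**What to change.** **Primary outcome.** In SAP 7.5 (Primary Efficacy Outcome) and Protocol 3.16.2, name the already planned multivariable Cox adjusted hazard ratio as the sole test of superiority, two-sided 0.05, with no fallback that depends on the data. Fix its covariates in advance from baseline variables collected in all patients: age, sex, hypertension, diabetes, smoking, BMI, qualifying event type, time since the event, first or recurrent event, anterior or posterior circulation, ASPECTS/pc-ASPECTS, baseline mRS and NIHSS, and centre.

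**Roles of the other analyses.** Label the full-cohort log-rank test, Kaplan-Meier curves and univariate hazard ratio descriptive, and the matched analysis sensitivity. Use perfusion status and collateral grade only in sensitivity analyses. Protocol 3.6.1 specifies perfusion evaluation only for ICA and M1 occlusions. Collateral grade is read from DSA (Protocol 3.14), while CTA is enough for eligibility.

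**Secondary outcomes.** In SAP 7.7 (Secondary Outcomes), adjust the full-cohort 1-year mRS model for baseline mRS and the same covariates, and use the same covariates for EQ-5D. The gap is smaller here, because the matched analysis already reaches these outcomes.

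**Interpretation.** State that unmeasured confounding remains and that the adjusted result is an association. Because the SAP uses the numbers 7.5, 7.6 and 7.7 twice, cite sections by title.

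**Cost.** Wording only; no new data. In simulation the standard error of the log hazard ratio was about 3-11% larger than the unadjusted one. Type I error is slightly liberal if events are few for the number of covariates: 5.0-6.8% with about 20 covariate terms and 48 events, and 7.0% with 30 events.
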